1. PROJECT TITLE

Project Title: A Prospective, Non-Randomized Study to Evaluate the CIRCA Esophageal Temperature Monitoring System in Prevention of Esophageal Lesions Following Atrial Fibrillation Radiofrequency Catheter Ablation

4. ESTIMATED DURATION OF THE STUDY

12 months

5. LAY LANGUAGE SUMMARY OR SYNOPSIS (no more than one paragraph)

One rare but potentially fatal complication of radiofrequency catheter ablation (RFCA) with the use of the Circa™ monitoring system is the development of atrio-esophageal fistula due to thermal injury of the esophageal tissues. The Circa™ temperature monitoring probe and temperature monitoring system are currently used in RFCA procedures here at UCSD to monitor thermal output in an effort to reduce the risk of complications due to thermal injury. This study is being conducted to determine the short-term effects of radiofrequency AF ablation with the use of the Circa™ monitoring system on the esophageal (swallowing tube) lining the day after AF ablation. Patients who choose to participate will receive an esophagoscopy the day after the ablation procedure to identify the presence or absence of esophageal lesions (number and size) reflecting damage to the lining of the esophagus.

6. SPECIFIC AIMS

To evaluate the effects of left atrial endocardial radiofrequency catheter ablation for AF, guided by the newly designed Circa™ esophageal temperature probe and monitoring system, on formation of esophageal thermal lesions with post-ablation esophagoscopy.

7. BACKGROUND AND SIGNIFICANCE

Radiofrequency catheter ablation (RFCA) for treatment of AF has been performed for nearly 15 years, but is associated with a small percentage of complications, including the rare but potentially fatal atrio-esophageal fistula. In patients where the esophagus traverses the left atrium near posterior left atrial endocardial ablation sites, it is thought that thermal injury to the atrial and esophageal wall may lead in rare cases to the formation of an atrio-esophageal fistula, which can lead to fatal gastrointestinal hemorrhage, or fatal systemic embolization causing stroke and/or cardiac arrest. The diagnosis of atrio-esophageal fistula after ablation has unfortunately most commonly been after one of these fatal events, but earlier recognition of this rare complication based on symptoms, fever, transient bleeding or embolic events, has led to use of esophageal stenting, or emergency thoracic surgery, which can be life-saving in some cases.

Due to the rarity of this complication, systematic study of its cause(s) is impossible, but in order to avoid it, it has been recommended in guidelines that ablation power and duration on the posterior left atrial wall be empirically limited, and in some cases esophageal position is marked by a barium swallow, or esophageal temperature and position can be monitored by a naso-gastric tube with an embedded temperature sensor (typically a single sensor in the past).

Recently a multi-sensor (12 sensors) temperature monitoring probe (Circa™) has been developed and FDA approved, that can be placed in the esophagus (while the patient is under general anesthesia) and positioned

under fluoroscopy directly posterior to the left atrium during RFCA for AF or left atrial flutter (LAAFL). This multi-sensor probe has the theoretical advantage of monitoring temperature at multiple locations in the esophagus (cranial to caudal temperatures spanning the left atrium are simultaneously displayed on monitor) during ablation, warning the operator of impending temperature rises during ablation and allowing ample time to terminate ablation and prevent esophageal heating above a target temperature of typically 38-39°C. Limiting esophageal heating to this maximum level of temperature may prevent potentially serious thermal injury to the esophagus that could lead to potentially fatal atrio-esophageal fistula.

In the electrophysiology laboratories at UCSD, where we have performed RFCA for AF and LAAFL for nearly 15 years, in several thousand cases, and to our knowledge have had possibly 1 or 2 atrio-esophageal fistulas (presumed but not confirmed) develop in our patients, over a decade ago. These patients were treated at outside hospitals for associated comorbidities however, which were fatal, and the diagnosis was thus only suspected and not confirmed. Since that time we have always monitored esophageal position and temperature, and then for the last several years since its FDA approval, we have used the Circa™ temperature probe in all our patients and have had no reported cases of atrio-esophageal fistula. We recently began using a newly designed Circa™ probe (see Figure for old and new probe shape) with good results, and plan to evaluate its success in preventing esophageal thermal lesions as well.

Previous studies have suggested that even when one reduces power during ablation at the posterior left atrium and monitors temperature, approximately 27% of patients will develop some evidence of esophageal thermal lesions (including endothelial esophageal ulcers or mediastinal changes). In addition, one center reports an even greater number of lesions observed when using the Circa™ probe during RFCA (although in this study power delivery and temperature were not modulated based on the temperature monitoring during ablation).

In contrast, we believe that due to its sensitivity and ability to monitor esophageal temperature at multiple locations spanning the atrium, use of the Circa™ probe should result in fewer or no esophageal thermal lesions, if esophageal temperature measured by the Circa™ probe is used to guide power delivery and duration of ablation on the posterior left atrial wall.

8. PROGRESS REPORT

There is a paucity of data in patients on the value of temperature monitoring during RFCA for AF to reduce thermal esophageal injury. However, during the routine clinical use of the device in several hundred cases over the past few years we have clinically observed a marked reduction in ablation time and power delivery in the posterior left atrial wall as compared to prior years before FDA approval of the Circa™ device.

In addition, in some patients we have been unable to ablate critical areas in the left atrium due to such temperature rises observed on the Circa™ probe, and have resorted to having the GI service attending/fellow move the esophagus with an endoscope to the right or left away from the critical ablation sites, thus allowing normal power delivery to achieve transmural atrial ablation and cure AF.

Thus, we believe that by using the Circa™ probe, to guide and limit power delivery and duration of ablation on the posterior left atrial wall, to avoid excessive esophageal temperature rises, and yet successfully complete the ablation, we will limit the potential for any esophageal thermal injury that might lead to an atrio-esophageal fistula.

We have recently completed a non-randomized esophagoscopy study in 20 patients, in whom AF ablation was performed while using the Circa™ probe to monitor and limit luminal esophageal temperature (LET), and thus prevent esophageal thermal lesions. We observed a single possible esophageal thermal lesion in only one patient

undergoing ablation (see progress report Table). This is significantly less than that typically observed in such patients according to previously published studies.

9. RESEARCH DESIGN AND METHODS

Study Design:

This will be a non-randomized, prospective, single-centered clinical trial. Twenty-five consecutive patients who agree to enroll in the study will undergo their clinically indicated AF ablation, during which all patients will be monitored using the newly designed Circa™ esophageal temperature probe, to prevent luminal esophageal temperature (LET) from rising above 39°C. The day following ablation, patients will undergo esophagoscopy before being discharged from the post-operative recovery area (PTU), in order to determine if there is any evidence of esophageal lesions that might be due to thermal injury.

The gastroenterologist performing esophagoscopy will be blinded to any intra-procedural data during the atrial fibrillation ablation, specifically any data relating to esophageal position during the ablation procedure, any observed temperature rises, and the power and duration of radiofrequency energy delivery during the ablation.

Following endoscopy, all patients will remain in the PTU until recovered from sedation, and when standard criteria are met they will be discharged directly to home and followed up in the outpatient arrhythmia clinic in the same manner as all other patients undergoing AF ablation at UCSD. This routine follow-up process is described to the patient prior to ablation as part of his/her clinical consent for the procedure, and does not involve any research procedures related to this study.

Methods:

The only research component of this study is the post-ablation esophagoscopy which is not standard of care for patients receiving RFCA for atrial fibrillation. The day following the patient's AF ablation, provided there have been no complications and vital signs are stable, he/she will undergo esophagoscopy under sedation, as is standard of care. During this procedure all vital signs will be monitored in a standard manner as they had been during the AF ablation, and the esophagus inspected in a standard manner for any evidence of lesions that might be due to thermal injury. Photographic evidence will be obtained and stored on disk of any lesions observed. A written description of the findings will also be provided by the gastroenterologist in his report of the procedure. Following esophagoscopy the patient will be monitored for the appropriate time to ensure stability of vital signs, and then patient will be discharged home when appropriate criteria are met.

The patient will be provided written instructions, as to allowed and disallowed activities following ablation and endoscopy, as they would normally be provided for any clinically indicated procedure.

There will be no other research related procedures or follow-up required for this study.

10. HUMAN SUBJECTS

A total of 25 patients will be recruited from the Cardiology Electrophysiology clinics and PTU, in order to account for any withdrawal. There will be no discrimination in enrollment based on gender or ethnic background. We expect the population of enrolled subjects to reflect similar percentages for gender and ethnicity as the overall population of patients receiving CIED procedures at UCSD. Patients will be approached and consented for the post-ablation esophagoscopy prior to AF ablation. If the eligibility of the subject changes between the time the subject is consented and the procedure, the subject will be considered a screen failure and the subject's participation will not be counted towards accrual for the study. It is the patient's

choice to withdraw from this study at any time before the esophagoscopy, or prior to ablation, without effect on his/her usual clinical care.

Inclusion Criteria: (all must be met)

1. Must have atrial fibrillation and be scheduled for AF ablation.
2. Must agree to esophagoscopy under sedation the next day in order to determine if there is any evidence of esophageal thermal injury.
3. Must give written informed consent.
4. Must be at least 18 years old

Exclusion Criteria: (presence of any one or more)

1. Patient's refusal to participate in the study.
2. Any known esophageal disease or prior injury that would preclude esophagoscopy.
3. Any complications occurring during or after AF ablation that would result in esophagoscopy being an added significant risk to the patient beyond the known potential risks from the esophagoscopy itself.
4. Prior AF ablation

2

Patients seen in the UCSD cardiac arrhythmia clinic or hospital inpatients, who are referred for consideration of AF ablation, will be evaluated to see if they meet enrollment criteria by [name] and/or the co-investigators. Medical records of potential patients will be screened prior to enrollment to ensure eligibility. If eligible, they will be asked if they would like to participate in the study. All patients will be under the care of the cardiac electrophysiology group at UCSD Medical Center.

A partial waiver of HIPAA and waiver of consent will be needed to screen medical records of patients of Sulpizio Cardiovascular Center to determine study eligibility. The partial waiver of HIPAA and waiver of consent for recruitment are necessary to ensure that patients who are approached for the study meet all inclusion and exclusion criteria in addition to reaching the enrollment goal for the study. The medical records of patients in UCSD cardiac arrhythmia clinic will be screened to assess eligibility for the study. Patients who have been determined to be eligible will be recruited in clinic or PTU by [name] or his research staff. The privacy risk to patients is minimal as all PHI collected for screening purposes will be stored in a password protected document in a limited access drive on the UCSD secured computer system. The waiver of consent and partial waiver of HIPAA will not adversely affect the rights and welfare of the potential subjects as only the minimal PHI necessary to determine eligibility will be collected for screening. This would include name, age, procedure type, procedure dates, medical record number, and medical information indicating satisfaction of the inclusion and exclusion criteria for the study. This will also benefit patients by reducing the likelihood of ineligible patients being consented to participate in the study or that patients are approached more than once to participate. Only [name] and his research staff will have access to the PHI and will be involved in the screening process. As soon as recruitment for the study is complete, identifiers for all screened patients who did not enroll in the study will be destroyed or deleted from our system. The only information that will be retained from screened patients will be information necessary for publication, including reason for study exclusion and date the patient was screened. If at any point during the study, there is a change in the risk to benefits ratio affecting a patient's safety or willingness to participate, those enrolled or screened (as applicable) will be notified. There will be no advertising (brochures, flyers, posters, etc.) used in recruitment for this study.

12. INFORMED CONSENT

Patients must sign the most current IRB approved informed consent form prior to any study related procedures. Only the principal investigator, sub-investigators, or research coordinators will obtain informed consent, after

complete explanation of the nature and purpose of this study. The consent for this study will be signed by the subject and the individual obtaining informed consent.

13. ALTERNATIVES TO STUDY PARTICIPATION

The alternatives to participation in this study are to not participate in the study and to continue to receive standard care AF ablation. Standard of care for RFCA ablation for atrial fibrillation would not include post-ablation esophagoscopy.

14. POTENTIAL RISKS

The published literature indicates that there are known risks during routine esophageal endoscopic procedures including:

Minor irritation leading to a sore throat, and major complications including esophageal perforation leading to potential mediastinal infection and death, the potential need for surgery to repair a perforation, and major traumatic injury leading to bleeding.

Although every effort will be undertaken to maintain confidentiality, there is a risk of possible loss of participant's confidentiality.

Radiation Exposure:

Fluoroscopy is used as standard of care throughout the ablation including placement of the CIRCA monitoring system and is not affected by the research study (as the endoscopy does not require radiation). Each patient will only undergo the RFCA procedure once. The RFCA can take up 4-8 hours, average fluoroscopy time for [name] ablations are 40 minutes and can run up to about 60 minutes. This will be the same regardless of study participating. The estimated radiation exposure for this procedure is 70.4mSv.

15. RISK MANAGEMENT PROCEDURES AND ADEQUACY OF RESOURCES

After AF ablation and endoscopy, patients will be monitored in the PTU, including vital signs, until all criteria are met for patient discharge. The PTU is a fully staffed, licensed facility where all recovery from AF ablation is currently routinely clinically performed during a patient's overnight stay, and where all trans-esophageal echocardiograms (similar procedure to esophagoscopy) and cardioversions are also currently performed safely and effectively.

The cardiac arrhythmia clinic is staffed by nurse practitioners, attendings and fellows, for procedural related issues. The clinic number [contact] is answered daily from 8 AM to 5 PM, and the nurse practitioners are always available during this time period. The nurse practitioners discuss all phone calls with the primary cardiac electrophysiologist and make notes into the EPIC electronic medical record. After business hours, the answering machine provides the number for the electrophysiology fellow and attending on call, who are available 24 hours daily for urgent issues. Or the patients can call the page operator to reach a fellow or attending with questions at [contact].

The research staff, also, will be monitoring patients during the study procedure and prior to discharge for adverse events. All adverse events will be reported according to current IRB requirements.

The Research Coordinator in the cardiac electrophysiology division who can assist with the reporting of any adverse events to the Human Studies Committee.

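### Active research monitoring for adverse events ends at discharge after the research-only esophagoscopy, so delayed harms and the later course of lesion-positive patients are not systematically collected as study data

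*Protocol*

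**What the plan says.** Protocol Section 15 describes what research staff do about safety: "The research staff, also, will be monitoring patients during the study procedure and prior to discharge for adverse events". Section 9 fixes when that window closes. After endoscopy, "all patients will remain in the PTU until recovered from sedation, and when standard criteria are met they will be discharged directly to home". The esophagoscopy takes place the day after ablation, so discharge falls on the day of the esophagoscopy and not on the day of the ablation.

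For the time after discharge, Section 9 states: "There will be no other research related procedures or follow-up required for this study". Patients are then "followed up in the outpatient arrhythmia clinic in the same manner as all other patients undergoing AF ablation at UCSD", and the protocol adds that this routine process "does not involve any research procedures related to this study".

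Section 15 also provides a daytime clinic line, whose calls are discussed with the electrophysiologist and noted in the clinical record, and an on-call fellow and attending "who are available 24 hours daily for urgent issues". It commits to reporting adverse events as the IRB requires and gives no end date for doing so.

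Section 9 identifies the esophagoscopy as the study's sole research component and as outside standard care. Among its known risks Section 14 lists "major complications including esophageal perforation leading to potential mediastinal infection and death", as well as possible surgical repair and bleeding from traumatic injury. Section 17 directs patients with significant lesions to clinical care. The SAP has four general items and no safety or lesion-outcome summary.

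**The concern.** The participant undergoes an invasive procedure only because of the study, so any harm from it is a harm of the study. Several of the harms in Section 14, such as perforation with later mediastinal infection, need not be evident by the time a patient has recovered from sedation. If research staff look for events only until discharge and no later research contact is planned, a delayed event is found only when the patient reports it or a clinician notices it.

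The same applies to patients with a lesion. Section 18 says that finding a lesion early could lead to treatment and possibly prevent progression, but no data item records what happened to such a patient afterwards. For fistula, a complication of the ablation, Section 7 refers to "earlier recognition of this rare complication based on symptoms, fever, transient bleeding or embolic events". These are signs that a scheduled question after discharge could pick up and that a window closing at discharge could not.

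At stake are the completeness of the harm report from 25 volunteers and the interpretation of any lesion found. The day-after lesion result itself is not at stake.

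**Working it through.** The documents give no complication rate, safety target or power statement, so there is no planned figure to reproduce. The main check is a reading of the text; the arithmetic only gives scale.

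**Step 1: what each provision does after discharge**

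| Provision | Where | Actively seeks events? | Route into study data described? |
|---|---|---|---|
| Research staff monitoring | Protocol 15 | Yes, until discharge | Not stated |
| Other research follow-up | Protocol 9 | None required | None |
| Arrhythmia clinic follow-up | Protocol 9 | Clinical care; schedule not given | No; described as not research |
| Clinic line and on-call cover | Protocol 15 | No; the patient must call | No; clinic-line calls noted in the clinical record |
| Reporting under IRB rules | Protocol 15 | No method of finding events given | Reporting duty only, no time limit |
| Care for significant lesions | Protocol 17 | Clinical care | No outcome item |
| Analysis | SAP | Not applicable | No harm or lesion-course summary |

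After discharge there are ways for an event to become known and be reported. None of them is a planned search, and none is linked to a study variable or a table.

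**Step 2: patients with a lesion whose later course is not a data item**

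Inputs: N = 25 (Sections 9 and 10); about 27% from previous studies (Section 7); 1 possible lesion in 20 patients in the centre's own earlier series (Section 8).

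- At 27%: 25 × 0.27 = 6.75 patients expected.
- At 1/20: 25 × 0.05 = 1.25 patients expected.
- Chance of at least one at the lower rate: 1 − 0.95^25 = 0.723, or 72%.

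The 27% includes mediastinal changes, which inspection of the esophageal lining may not show, so 6.75 is best read as a high figure.

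**Step 3: what a zero count would mean**

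With 0 events in n patients, the exact two-sided 95% upper limit is 1 − 0.025^(1/n).

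- n = 25: 1 − 0.025^(1/25) = 13.7%.
- n = 20 (assumed; Section 10 allows for withdrawals but gives no rate): 1 − 0.025^(1/20) = 16.8%.

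As the plan stands, the systematically observed period behind such a zero ends at discharge.

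**Step 4: chance that a delayed event occurs at all**

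The per-patient risk p of an event first appearing after discharge is assumed, since the documents give none. The chance of at least one in 25 is 1 − (1 − p)^25.

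| Assumed p | Chance of at least one in 25 |
|---|---|
| 0.1% | 2.5% |
| 0.5% | 11.8% |
| 1% | 22.2% |
| 2% | 39.7% |

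Throughout this range the most likely number of delayed events is zero. The case for the change therefore rests on Steps 1 and 2 and not on an expectation that an event will occur.

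**The case against.** The strongest reply is that events after discharge are already covered. The commitment to report adverse events under IRB rules has no time limit, and a research coordinator assists with it. The same electrophysiology group cares for these patients, calls to the clinic line are discussed with the electrophysiologist, and Section 16 gives patients a research-team contact. The sentence on research staff says that they *also* monitor, so it adds to clinical surveillance and does not define when events cease to count.

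Much of this stands. A reader might infer that nothing seen in clinic can enter the study. The documents do not say so: they state that clinic follow-up involves no research procedure and that no other research follow-up is required, and neither statement bars recording an event that the team learns of. What remains is the difference between being able to report an event and looking for one. The centre's own history in Section 7 illustrates it: the one or two suspected fistulas were in patients treated at other hospitals, and the diagnosis was never confirmed.

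A second reply is that the aim is lesion formation at day-after endoscopy. Neither lesion course nor procedural safety is an aim, and Section 7 accepts that fistula is too rare for systematic study. This also stands, and it limits the point: no efficacy conclusion changes. It does not remove the reason to follow up the harms of a procedure done only for research.

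A reader might also infer that the study will be unable to support the statement in Section 18 that the risk of esophagoscopy is low. That statement is an advance justification. It refers back to Section 14, which relies on published literature, and the study is not offered as evidence for it. With an upper limit of 13.7% at 0/25, the study could not establish a low risk even with complete follow-up.

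**Conclusion.** The point holds in a limited form. Active research monitoring stops at discharge, after recovery from the research-only esophagoscopy on the day after ablation, and no later research contact is required. Delayed harms named in the protocol are therefore not actively sought, and neither they nor the later clinical course of lesion-positive patients are planned as study data or summarised in the SAP. It would go too far to say that patients have no contact after discharge or that delayed events must go uncounted, because clinical follow-up, telephone cover and the reporting commitment are all in the protocol.

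On size, the expected number of patients with a lesion and no recorded later course is 1.25 to 6.75 of 25, assuming that the protocol's cited rates apply here. The number of delayed harms cannot be estimated from the documents. This is an inexpensive improvement to harm reporting and patient safety. It is not a flaw in the lesion endpoint, and the safety data would remain descriptive after the change.

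**What to change.** 1. **Protocol Section 15.** Extend adverse-event ascertainment past discharge by one coordinator telephone call at a fixed time stated in advance, and by abstraction of the arrhythmia-clinic note and chart that routine care already produces. Ask specifically about care received at other hospitals.
2. **Data items.** Record esophageal symptoms, bleeding, infection, readmission and suspected fistula. For lesion-positive patients also record the clinical course. A call or a chart note cannot show endoscopic healing, so the item should not be labelled as healing.
3. **Protocol Section 9 and consent.** Amend the statement that no other research follow-up is required, and the consent wording, to match.
4. **SAP.** Add a descriptive count of each harm with its exact 95% confidence interval, the number of patients actually reached, and the observation window. List harms of the esophagoscopy separately from complications of the ablation where they can be told apart.

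The cost is about 25 calls, 25 chart abstractions and the wording changes, met by existing coordinators. No new visit or procedure is needed, and neither N nor the day-after lesion endpoint changes. The remaining limits are that the documents do not give the clinic schedule, so the abstraction window has to be stated, and that 25 patients can support description only.
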